In general, patients considered having high, long term risk of sudden arrhythmic death (SCD) receive implantable cardioverter-defibrillators (ICD).

Risk assessment in patients that are candidates for ICD therapy is difficult and time consuming, though. In order to bridge the time period necessary to identify the patient who will need an ICD or in whom ICD therapy is unnecessary, a tool is mandatory that protects the patient during this time period from dying suddenly and to provide continuous ECG monitoring which is necessary for the risk assessment.

The device that is able to fulfill these characteristics is the wearable cardioverter-defibrillator (WCD). The WCD has CE certification and is FDA approved since 2002. Currently, only observational studies with the WCD are available. Prospective randomized studies in patients that are already considered carrying a high risk of sudden death are difficult, if not impossible to perform, mainly due to ethical reasons.

Currently available data with the WCD demonstrate that the WCD is safe and effective. Detected ventricular tachyarrhythmias are terminated with the first shock in 98% of all cases; inappropriate defibrillator discharges (not occurring on sustained VT or VF) may occur in <1% per month of WCD wearing⁹.

3. Risks and benefits of the investigation

Patients participating in the post-market clinical follow-up study in France will have neither additional risks due to participation in the study compared to clinical routine care nor individual benefits, because of its purely observational character.

4. Objectives and hypotheses of the investigation

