5.3.1.5 Data extracted from the LifeVest Network

- Wear time (hours per day)
- Description of all delivered treatments and associated ECG
- Description of asystole, detected arrhythmia with no treatment (e.g., short run of VT) and associated ECGs
- Information about any technical malfunctions and misuses, if applicable

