4.1 Primary study objectives

1. **Appropriate shocks** as measured by shocks delivered for adjudicated sustained ventricular tachycardia (VT) or ventricular fibrillation (VF) episodes.
2. **Inappropriate shocks** as measured by shocks delivered for all episodes that are not adjudicated sustained VT or VF episodes.

The frequency and rate of appropriate and inappropriate shocks will be measured. The risk of receiving an inappropriate shock will be analyzed. The risk of not receiving appropriate shocks when necessary will also be analyzed.

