12.1 Primary parameters

- Arrhythmic (VT/VF) events and characterization of event:
 - Number of WCD shocks until termination of the tachycardia event
 - Cardiac arrest immediately after shock delivery
 - Asystole after VT/VF event
 - Maximum heart rate during ventricular tachycardia
 - Polymorphic VT event
 - Immediate ventricular fibrillation (VF)
 - Ventricular tachycardia degenerating into ventricular fibrillation (VF)
- Efficacy will be evaluated using the success rate of appropriate shocks: Number of VT/VF events terminated by shocks/VT/VF events with shock delivery
- Rate of treated VT/VF episodes calculated as shocked VT and VF events/ all VT and VF events
- Cumulative probability of sustained VT/VF, determined according to the Kaplan-Meier method in function of time
- Number of arrhythmic events and shocked events
 - Within 30 days from activation date
 - Within 90 days from activation date

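### The SAP specifies no rate of appropriate or inappropriate shocks per unit of wear time, although wear time depends on indication and is already recorded

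*Combined protocol and SAP*

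**What the plan says.** - **Objective.** Protocol 4.1 and SAP 4.1 both state: "The frequency and rate of appropriate and inappropriate shocks will be measured".
- **SAP 10 (primary analysis).** It plans a quantitative analysis of each shock type without naming a measure, denominator or interval. It defines two ratios: missed shocks over VT/VF events, and inappropriate shocks over non-VT/VF events.
- **SAP 12.1.** It lists "Rate of treated VT/VF episodes calculated as shocked VT and VF events/ all VT and VF events", a success ratio that is also per event, and "Number of arrhythmic events and shocked events" in two windows, the first being "Within 30 days from activation date" and the second 90 days. It also lists "Cumulative probability of sustained VT/VF, determined according to the Kaplan-Meier method in function of time".
- **SAP 8 and 9.2.** Patients with WCD events are described over the wearing period, including whether a shock was delivered and whether it was appropriate. Nominal variables are given as number and percentage of patients.
- **SAP 11 and 12.2.** WCD events, and the 12.1 parameters, are tabulated by indication.
- **Protocol 2.** As background from earlier data, inappropriate discharges "may occur in <1% per month of WCD wearing".
- **Wear.** Protocol 5.1.1 expects a mean of three months, from one month up to six in some indications, and until transplant or ICD for listed patients. Protocol 5.2.8 says that duration depends on indication. Daily wear hours are extracted from the device network (protocol 5.3.1.5), and SAP 14 analyses wearing period and daily use, but only as usage.

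**The concern.** None of the specified shock outputs divides by time worn. The ITT set takes in every consenting patient whatever the length of wear (SAP 6.1), so a 90-day count combines patients who stopped after days with patients exposed for the whole window. Counts and percentages of patients grow with exposure. An indication with long wear will therefore show more shocks than one with short wear even if the underlying risk is the same. The per-event ratios do not fill the gap, because they describe what the device does once an event is detected and not how often a wearer is shocked.

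Two things are at stake: the comparison of shock outcomes across indications, and the reader's ability to set the inappropriate-shock result beside the only time-based shock figure that the protocol quotes. Leaving the measure in SAP 10 open also allows the denominator to be chosen after the data are seen.

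**Working it through.** **1. The plan's own figure.** SAP 5 gives a precision of 0.8 points at 1% and 1.8 points at 5% for 550 patients. The formula is 1.96 × √(p(1−p)/n).
- p = 0.01, n = 550: 1.96 × √(0.01 × 0.99/550) = 0.83 points.
- p = 0.05, n = 550: 1.96 × √(0.05 × 0.95/550) = 1.82 points.

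Both agree with the SAP after rounding. With 1,200 patients they become 0.56 and 1.23. These are half-widths for a proportion of patients and say nothing about a rate over time.

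**2. Denominator of each shock output.**

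| Output | Denominator | Time at risk? |
|---|---|---|
| Quantitative analysis (SAP 10) | not stated | not stated |
| Missed shocks (SAP 10) | VT/VF events | no |
| Risk of inappropriate shock (SAP 10) | non-VT/VF events | no |
| Success and treated ratios (SAP 12.1) | VT/VF events with shock; all VT/VF events | no |
| 30- and 90-day numbers (SAP 12.1) | none | fixed window, no number at risk |
| Patients with a shock (SAP 8, 9.2) | patients | no |

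The only time-to-event estimate in SAP 12.1 is for sustained VT/VF. The other Kaplan-Meier curves in the SAP are for survival and end of use.

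**3. What exposure does to a percentage of patients.** Assume a constant hazard of 1% per month, the ceiling of the background figure. The cumulative proportion is 1 − exp(−0.01 × m).
- m = 1, 3, 6 months: 1.0%, 2.96%, 5.82%.
- Inside the 90-day window, m = 1, 2, 3 months: 1.0%, 1.98%, 2.96%.

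In the other direction, the monthly rate implied by a crude proportion p is −ln(1 − p)/m.
- p = 5%: 5.13%, 1.71% and 0.86% per month at 1, 3 and 6 months.
- p = 1%: 1.01%, 0.34% and 0.17% per month.

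A crude 5% can thus lie above or below 1% per month, depending only on wear. The 1% to 5% range in SAP 5 is for shock delivery in tachyarrhythmic events; it is used here to show the scale, not as a forecast of inappropriate shocks.

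**4. What the expected cohort could estimate.** SAP 5 expects about 1,200 patients. With mean wear of 3 months, exposure is 1,200 × 3 = 3,600 patient-months. At 1% per month that yields 36 events. The exact Poisson limits are χ²(0.025; 72)/2 and χ²(0.975; 74)/2, each divided by 3,600, which gives 0.70 to 1.38 per 100 patient-months. If mean wear were 1 month (12 events) the interval would be 0.52 to 1.75, and at 6 months (72 events) 0.78 to 1.26.

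**5. The exposure unit.** The protocol's introduction reports average use of over 21 hours per day. At 21 hours, 3,600 calendar months of wearing period are 3,600 × 21/24 = 3,150 months actually worn, and 36 events become 36/3,150 = 1.14 per 100. The unit has to be stated.

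**The case against.** The best defence is that this is a descriptive study whose documents often use the word rate for a proportion: the precision statement in SAP 5 and the treated-episode measure in SAP 12.1 are examples. On that usage, the percentage of patients with a shock meets the objective. That percentage is available for the whole wearing period, so shock reporting is not confined to the two windows. This stands: the objective does not clearly promise a rate per month. It does not make the percentages comparable across indications with different wear.

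Three stronger readings are tempting, and the documents do not support them.
- *Arrhythmia frequency is also reported only as raw counts.* It is not. SAP 12.1 plans a Kaplan-Meier estimate for sustained VT/VF, which allows for unequal follow-up if patients are censored at WCD withdrawal, as in the protocol's section 6 table. The gap concerns shocks.
- *A shock rate cannot be obtained.* It can. Wear hours are collected, and SAP 14 uses activation and end-of-use dates. What is missing is pre-specification.
- *Neither primary outcome can be compared with the protocol's benchmark.* The figure of under 1% per month is background, concerns inappropriate discharges only, and no objective or analysis sets a formal comparison with it. The documents give no per-month figure for appropriate shocks.

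A further fair point is that the device can deliver up to five shocks, so discharges may cluster within a patient and a simple Poisson interval on all shocks would be too narrow. The fix allows for this.

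**Conclusion.** The point holds for appropriate and inappropriate shocks only. As specified, their counts and percentages mix exposure with risk when tabulated by indication, and no pre-specified shock analysis is on the per-month scale that the protocol quotes for inappropriate discharges. The possible distortion is about sixfold in the percentage of patients with a shock between one and six months of wear (1.0% against 5.8%) at the same underlying rate.

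That size rests on a constant hazard and on 1% per month, which is the ceiling of the quoted figure. The interval of 0.70 to 1.38 per 100 patient-months further assumes 1,200 patients, mean wear of three months, and at most one counted event per patient. These figures illustrate the scale; they do not measure an error in a stated result. This is a cheap improvement and does not call the design into question.

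**What to change.** Add to SAP 10 and 12.1, separately for appropriate and inappropriate shocks, overall and by indication:

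- (a) patients with at least one shock per 100 patient-months, with exposure counted from activation to first shock or end of use, and an exact Poisson 95% interval;
- (b) all shocks per 100 patient-months, with a 95% interval that allows for repeat shocks within a patient, for example from a robust variance or a patient-level bootstrap.

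State the exposure unit: wearing period from activation to end of use for the main result, with recorded worn hours as a sensitivity analysis. Give the number of patients still at risk beside each 30- and 90-day count.

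The cost is one extra table. No new data are needed.

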12.2 Secondary parameters

- Analysis of primary outcome parameters (section 12.1) in sub-groups according to their clinical profile at baseline:
 - Age:
 - < 40 years
 - $\geq 40 - < 65$ years
 - $\geq 65 - < 75$ years
 - ≥ 75 years
 - Gender
 - Indication of WCD:
 - implantable cardiac defibrillator (ICD) removal due to cardiac device infections,
 - a bridge to heart transplantation,
 - in the early post-MI period with left ventricular (LV) dysfunction (LVEF $< 30\%$),
 - a recent coronary revascularization with LV dysfunction (LVEF $< 30\%$).
 - Type of inherited arrhythmia syndrome:
 - Long-QT syndrome (LQTS)
 - Brugada syndrome
 - Catecholaminergic polymorphous ventricular tachycardia (CPVT)

- Arrhythmogenic right ventricular cardiomyopathy
- Other
- Unknown

In addition the following parameters will be analysed in the mentioned subgroups:

- Cause of death (as assessed by CEC)
- Hospitalization
- Type of SAE

LV-EF at baseline and at time of WCD end of use

13. On-treatment efficacy analysis

For on-treatment efficacy analysis, tables on baseline characteristics and outcome will be shown comparing patient group on-treatment to not on-treatment (for definitions refer to 6.3).

14. Analysis of WCD usage on ITT population

Analysis of usage patterns will be done by:

- Description of WCD wearing profile:
 - Average prescription period
 - Average wearing period (date of activation to date of end of use)
 - Average wearing period by gender
 - Description and analysis of compliance of WCD wearing: WCD device in use during wearing period (days in use / number of days of wearing period) Average daily WCD usage (hours)
- Regression model/ANOVA evaluating factors influencing the non-compliance of patients with prescribed WCD (age, gender, neurologic function, co-morbidities etc.)
- Distribution of reasons for end of WCD usage
- Kaplan-Meier curves for time to end of WCD usage.

15. Missing values

Missing data will not be replaced by any algorithm.

16. Applied software

R (version 3.3.3 or later)

17. Literature

- 1) Myerburg RJ. Sudden cardiac death: exploring the limits of our knowledge. *J Cardiovasc Electrophysiol* 2001; 12:369-81.

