5.2 Subjects

Study population will consist of patients at high risk for SCD and receiving LifeVest as a bridge therapy to heart transplantation, to ICD or to improvement of LV function.

5.2.1 Inclusion criteria for subject selection.

- Patients receiving a LifeVest prescription in clinical routine for the following indications:
 - a) implantable cardiac defibrillator (ICD) removal due to cardiac device infections,
 - b) a bridge to heart transplantation,
 - c) in the early post-MI period with left ventricular (LV) dysfunction (LVEF <30%),
 - d) a recent coronary revascularization with LV dysfunction (LVEF < 30%).
- Patients who have given their consent to participate.

This includes also those patients who have already completed use of LifeVest before start of the study in the corresponding study site (retrospective inclusion).

5.2.2 Exclusion criteria for subject selection.

There are no exclusion criteria for this study other than if the patient does not provide informed consent to participate. All patients prescribed a LifeVest will be invited to participate. All patients that were previously prescribed a LifeVest before the start of this study will also be invited to participate by allowing access to their retrospective medical information.

5.2.3 Criteria and procedures for subject withdrawal or discontinuation.

A low rate of lost-to-follow up is expected since the LifeVest is rented to patients and should be returned to ZOLL by the end of the prescription. In case a patient is lost to follow up, the CepiDC a French database for automated coding of causes of death, will be interrogated to report if the patient is dead or alive, and if dead the cause of death.

All patients enrolled into the study can withdraw at any time regardless of the reason. Patients may withdraw consent for use of data and exit the study at any time without prejudice to further treatment.

Patients who have given consent to participate in the study but had the WCD for less than 8 days will be evaluated separately, but not withdrawn.

5.2.4 Participating centers and point of enrolment:

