6.2 On-treatment population

Patients who have worn WCD for at least 8 days (i.e. longer than 1 week) will be evaluated separately in an “on-treatment” efficacy analysis, because it is assumed from clinical experience that the WCD wearing time will only be long enough for those patients to reliably compare their long-term outcome in a cohort of patients who have had the WCD for several months (even six or more months in some indications).

7. Analysis datasets

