9.2 Follow-up data (wearing period) of ITT population

The following follow-up data will be described:

- Serious adverse events since inclusion by number of events in groups of
 - Type of event
 - Cardiac arrhythmic
 - Cardiac non-arrhythmic
 - Vascular non-cardiac (including stroke)
 - Cardiovascular without clearly defined other cause
 - Non-cardiovascular
 - Related hospital stay/prolongation of existing hospital stay
 - Causal relationship to WCD
 - Intensity
 - Outcome
 - Criteria for seriousness
- Time to first hospitalization
- Death
 - Cardiovascular
 - Cardiac
 - Vascular non-cardiac (including stroke)
 - Cardiovascular without clearly defined other cause
 - Non-cardiovascular
 - Death during prescription duration
 - Death while wearing the WCD
 - Death related to arrhythmic event
 - Death related to WCD dysfunction
- WCD events

WCD events/patients with WCD events with following event parameters:

- Type of event
- Termination of event
- Response button pressed
- Shock delivered
- Shock appropriate/inappropriate
- Occurrence of technical and non-technical problems during the wearing period
- Return of WCD device (end of therapy) due to:
 - Death
 - ICD implantation
 - Heart transplantation

- LV function improvement
- Patient's wish
- Other reason
- Clinical status on WCD return: Most recent LV-EF value, NYHA classification, risk assessment and if patient is still listed for heart transplantation
- Planned therapy after wearing period:
 - ICD implantation
 - PCI (Angioplasty, Stent)
 - Bypass surgery
 - Implantation of cardiac pacemaker
 - Heart transplantation
 - Implantation LVAD (left ventricular assist device)
 - Therapy with anti-arrhythmic agents
 - Other planned cardiac therapy
- Medication on WCD return

10. Primary analysis on ITT population

1. **Appropriate shocks** as measured by shocks delivered for adjudicated sustained ventricular tachycardia (VT) or ventricular fibrillation (VF) episodes.

- Quantitative analysis of appropriate shocks
- Analysis of the risk of not receiving appropriate shocks when necessary, calculated as number of non-terminated VT/VF events without shock delivery and without response button pressed/ number of VT/VF events

2. **Inappropriate shocks** as measured by shocks delivered for all episodes that are not adjudicated as sustained VT or VF episodes.

- Quantitative analysis of inappropriate shocks

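### SAP 13 compares outcomes between patients who wore the WCD at least 8 days and those who did not, so early deaths help decide which group a patient is in

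*Combined protocol and SAP*

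**What the plan says.** SAP 6.2 defines the group: "Patients who have worn WCD for at least 8 days (i.e. longer than 1 week) will be evaluated separately in an" on-treatment efficacy analysis. The reason given is that only these patients have worn the device long enough to "reliably compare their long-term outcome in a cohort of patients who have had the WCD for several months". Protocol 5.1.2 says the same. Under protocol 5.2.3, consenting patients who "had the WCD for less than 8 days will be evaluated separately, but not withdrawn".

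SAP 13 turns this into a comparison: "tables on baseline characteristics and outcome will be shown comparing patient group on-treatment to not on-treatment". It names no outcome, time window, test, landmark or person-time denominator. Its pointer to 6.3 for the definitions leads nowhere, because the definition is in 6.2.

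Four other places bear on the point:
- Death is a listed reason for end of use (protocol 5.3.1.4, SAP 9.2).
- Participation ends when the LifeVest is withdrawn (protocol 5.2.8). Event-free patients followed to study end are censored on that date (protocol 6).
- SAP 9.2 lists two death windows, "Death during prescription duration" and "Death while wearing the WCD". Protocol 5.2.3 adds a mortality look-up: "In case a patient is lost to follow up, the CepiDC a French database" on causes of death, is queried.
- SAP 14 gives a clock that could define wear: "Average wearing period (date of activation to date of end of use".

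**The concern.** The grouping depends on what happens after activation, and the outcome is then compared from activation. Two distortions follow.

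- **Death.** A patient who dies in use before day 8 can only be not on-treatment. This holds whether wear means time to end of use or days actually in use. On-treatment patients cannot die in the first week by definition.
- **Time at risk.** For anything counted only while the device is worn (shocks, VT/VF, hospitalisation), the short-wear group has at most a few days of observation if wear means time to end of use. The on-treatment group has about three months.

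The section is titled an efficacy analysis, the study has no control group (protocol 14), and its data support a reimbursement renewal (SAP 7.2). Short wearers could easily be read as a comparator, and a table of deaths by these groups could look like an effect of wearing the device when there is none.

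**Working it through.** **The plan's own figure.** The only precision statement is for shock rates with 550 patients: 1.96 × √(0.01 × 0.99/550) = 0.83 points and 1.96 × √(0.05 × 0.95/550) = 1.82 points. These match the stated 0.8 and 1.8. Nothing is given for the SAP 13 contrast.

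**Inputs from the documents.** About 1,200 patients (SAP 5), wear of about 3 months (protocol 5.2.8), cut at day 8 (SAP 6.2), two-sided 5% tests as the general rule (SAP 8), shock delivery in 1% to 5% (SAP 5).

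**Assumptions.** 90-day mortality m of 1%, 3% or 5%, with a constant hazard unrelated to wear (no true effect). A proportion s of 2%, 5% or 10% stop before day 8 for other reasons, spread evenly over days 0 to 8. All others wear to day 90 or death.

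**Formulas, with m = 3% and s = 2%.**
- Daily hazard: λ = −ln(1 − m)/90 = 0.0003384.
- Death by day 8: p8 = 1 − e^(−8λ) = 0.002704.
- Not on-treatment: 1 − (1 − s)(1 − p8) = 1 − 0.98 × 0.997296 = 0.02265, or 27 of 1,200.
- Of these, died while wearing: (1 − s)p8 + s × 4λ (approximately) = 0.002650 + 0.000027 = 0.002677. Divided by 0.02265 this is 11.8%, about 3 deaths.
- Of these, died within 90 days, worn or not: p8 + s(m − p8) = 0.002704 + 0.02 × 0.027296 = 0.003250. Divided by 0.02265 this is 14.3%.
- On-treatment, both windows: 1 − e^(−82λ) = 2.7%.

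Results for s = 2% / 5% / 10%:

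| m | n not on-treatment | Not on-treatment: died while wearing | Not on-treatment: died within 90 days | On-treatment |
|---|---|---|---|---|
| 1% | 25 / 61 / 121 | 4.2 / 1.7 / 0.8% | 5.2 / 2.7 / 1.8% | 0.9% |
| 3% | 27 / 63 / 123 | 11.8 / 5.0 / 2.5% | 14.3 / 7.7 / 5.3% | 2.7% |
| 5% | 29 / 65 / 125 | 18.4 / 8.2 / 4.2% | 22.3 / 12.6 / 8.7% | 4.6% |

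**If a test were applied.** In simulated trials at m = 3%, Fisher's exact test at 5% rejects in about 55%, 20% and 3% of trials (while wearing) and 69%, 51% and 33% (90 days).

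**Person-time does not repair it.** A separate simulation let wear end at 30, 90 or 180 days (mean about 90). At m = 3% and s = 2%, deaths per person-day from activation were about 97 times higher in the short-wear group. Even at s = 10%, where the crude proportions nearly agree, the ratio was about 20. Comparing days 0 to 8 in all patients with time after day 8 in those still in use gave 0.97 to 1.03 in every scenario, as it should with no effect.

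**Days-in-use reading.** If wear means days in use, and each day is worn with assumed probability 0.7, the while-wearing case at m = 3% becomes 15.8%, 7.2% and 3.6% against 2.7%.

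**Shocks.** Mean observed time is about 4 against 89 days. With a proportion q shocked per 90 days, the proportion seen is about 1 − (1 − q)^(t/90). For q = 1%, 2% and 5% this gives 0.04%, 0.09% and 0.23% at t = 4, against 1.0%, 2.0% and 4.9% at t = 89. The gap comes from exposure alone.

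**The case against.** - **The outcome is not named.** Efficacy is defined as shock success (protocol 5.1.3, SAP 12.1), and that measure has no time-at-risk problem. This is fair as far as it goes. But SAP 6.2 speaks of long-term outcome and protocol 5.1.3 calls death the overall outcome, so death and event tables fall within SAP 13 as written.
- **Death and the other outcomes differ.** Only death has the survival-to-day-8 problem. For VT/VF and hospitalisation the issue is unequal observation, and the SAP has Kaplan-Meier methods for these. That stands as a distinction. SAP 13 promises plain tables, however, SAP 12.1 also lists simple counts, and Kaplan-Meier from activation does not cure the death problem.
- **Consent shrinks the effect.** Documentation starts at consent, so early deaths are the least likely to be enrolled. This stands. If half of first-week in-use deaths are lost at m = 3%, the short-wear figures become 1.6/25.6 = 6.3%, 1.6/61.5 = 2.6% and 1.5/121.4 = 1.3%, against 2.7%. Fisher rejection falls to roughly 17–21%, 2% and 5–6% while wearing, and to 35–38%, 22–23% and 13–14% over 90 days. If half of all deaths are lost, the while-wearing figures are 6.3%, 2.6% and 1.2% against 1.4%.
- **It is a supportive table.** True, and SAP 13 names no test, although the general rule in SAP 8 could supply one.

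**Conclusion.** The concern holds. As written, SAP 13 yields a distorted table for death and other time-at-risk outcomes, and nothing elsewhere in the plan corrects it. The mechanism follows from the definitions alone. Its size does not: the figures rest on assumed mortality, early stopping, constant hazard and enrolment of early deaths. Across the ranges shown without consent loss, the crude while-wearing death proportion in the short-wear group runs from slightly below to more than four times the on-treatment figure, on only about 1 to 5 deaths. Over 90 days it is always higher. Shock counts are biased in the opposite direction. This should be changed, but it is not critical: the study is descriptive, and the ITT analyses and shock success per shocked VT/VF event are not affected. The wrong cross-reference is clerical.

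**What to change.** In SAP 13:

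1. Keep the baseline table by group. Drop the between-group comparison of death, hospitalisation, event counts and other time-at-risk outcomes.
2. State that wear of at least 8 days means activation to end of use, the wearing period of SAP 14. Describe on-treatment outcomes from a day-8 landmark: patients alive and still using the device at day 8, later events only. Name the death window (while wearing, or prescription duration).
3. Give a separate descriptive table for patients under 8 days, as protocol 5.2.3 asks: events, follow-up time and reason for end of use, with no test or contrast.
4. Report first-week deaths and shocks for the whole ITT population.
5. Keep shock success per shocked VT/VF event, first-week shocks included.
6. Correct the cross-reference to 6.2.

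The cost is SAP wording and a little extra tabulation, with no new data. First-week events leave the on-treatment description but stay in the ITT and short-wearer tables.
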